1.2 Research Significance

Exposure to per- and polyfluoroalkyl substances (PFAS), recognized as "forever" chemicals due to their persistent nature, poses a significant threat to public health. With more than 98% of Americans having detectable levels of PFAS in their blood, these compounds have been linked to immune suppression by observations of increased infectious disease risks and diminished antibody response to vaccination, including routine tetanus-diphtheria vaccination in children [1-15]. Previous studies have demonstrated differences in the time course of production of specific IgG following tetanus-diphtheria (Td) vaccination in a small study of 12 adult participants over 7 time points in a 30-day period [6]. The proposed study will focus on exposure to Perfluorononanoic acid (PFNA) in Paulsboro, NJ, and add measurement of innate immune responses following the vaccine stimulus. The results of this study will increase knowledge about immunotoxicity resulting from PFAS exposure, which has been determined to be the critical effect for human health risk assessment by the U.S. EPA (Environmental Protection Agency) and EFSA (the European Food Safety Authority) [16,17]. The most recent scientific reviews of immunotoxic PFAS endpoints highlight the need for more relevant longitudinal human studies, and probing the immune response through vaccination has been a standard approach [18-20]. We will measure several markers of immune response in serum and oral fluid samples using standard immunoassays and targeted metabolomic analysis. An innovative aspect of our approach is the pilot testing of oral fluid collection as a less burdensome method, compared to venipuncture, for serial measurement of immune responses in epidemiological studies. Oral fluid (OF) is a biofluid that is a mixture of saliva and non-salivary components, which contains both innate and adaptive immune components, including specific immunoglobulins and cytokines [21-30]. OF has been shown to be a reliable biomatrix for detecting antibodies that represent serum concentrations, even though antibodies in this fluid are often found in lower concentrations when compared to serum. If found to be feasible and reliable in this study, this method will be useful in future community-based studies of immune response where repeated blood draws can often be a major barrier. Overall, this research project is crucial step in developing rational and effective measures to protect public health in the face of widespread PFAS exposure.

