
1.3 Research Design and Methods

HRP-503a-TEMPLATE-Interventional Research Protocol 1.11.22

Protocol Title: PFAS Exposure and Immune Response

Protocol Version: 3

Protocol Version Date: July 11, 2024

PI: [name], MPH, CIH, DABT

This study is a pre-post clinical trial. We will assess the impact of PFAS immune responses to routine booster vaccination against Tetanus-Diphtheria (Td) over a 30-day period among 20 adults recruited from a community in New Jersey that had drinking water contaminated with PFAS, predominantly PFNA. Within the larger study, 775 adults had serum PFAS measurements between July 2021 and September 2023. ("Human health effects of drinking water exposures to per- and poly-fluoroalkyl substances (PFAS): A multi-site cross-sectional study", Pro2020001052). For this study, we will recruit participants from the participants in the larger study who agreed to be contacted for future studies.

A. Research Procedures

All study visits will take place in the local Rutgers study office space ([name]) used for the main study. At study visit 1, participants will then have their blood drawn (15 mL) by venipuncture by trained research staff. Total amount of blood collected at visit one will be 15 mL (1 tablespoon). Participants will self-administer their oral fluid collection using the Oracol sampler (<https://www.malmed-oracol.co.uk/products/oracol/>) by swabbing their gumline for 1-2 minutes under the supervision of research staff. After baseline sample collection, participants will be given a Td booster vaccination. The second, third, and fourth study visits will occur 24, 48, and 72 hours after the first visit to capture the innate immune response, while visits five, six, and seven will take place 7, 14, and 30 days after the first visit to capture the adaptive immune response. At study visits 2-7, participants will have venous blood drawn (15 mL each visit) and will collect their oral fluid using the Oracol sampler by swabbing their gumline for 1-2 minutes under the supervision of research staff.

Additionally, data collected about the subject collected in the main study (including serum PFAS levels, residential history, and history of Td vaccination) will be used in this study.

B. Data Points

Td specific antibody levels, cytokine levels, CRP, RNA transcripts and metabolites related to immune response and activation.

C. Study Duration

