1.4 Preliminary Data – NA

1.5 Sample Size Justification

Twenty subjects will be enrolled. Identifying exposures predicting immune and disease outcomes requires sufficient power to account for false positives due to multiple comparisons. The goal of 20 adult subjects for the vaccination study was selected after statistical power calculations using data from the modeled Kielson (2016) study were done. Assuming the Kielson et al. correlation of 0.761 between PFAS level and change in diphtheria antibody concentration, then 20 subjects we would have 98.5% power to detect that the correlation is different from zero. Thus, we should have adequate power to detect effect sizes similar to those reported by Kielson even with some attrition and participant drop out. We may see a larger correlation as we expect a larger spread in our distribution of PFAS, yielding greater power. However, even with a smaller correlation of 0.7, we would have 95% power.

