1.8 Specimen Collection

A. Primary Specimen Collection

- **Types of Specimens:** Blood and oral fluid samples. At each visit, blood samples (15 mL) will be collected using standard venipuncture performed by a phlebotomist. Oracol swabs will be used to harvest oral fluid rich with GCF (and will be self-collected by the participant under the direction and supervision of research staff by gently swabbing their gumline for 2 minutes. In total there will be 280 specimens collected for this study (7 blood samples + 7 saliva samples per subject x 20 subjects). All specimen collections will happen at the local study site, [name].
- **Annotation:** The blood and oral fluid samples will be labeled by a study ID and visit number. The same study ID will be used for samples/data collected in the main study as in the supplemental study.
- **Transport:** The blood and oral fluid samples will be collected at the Paulsboro Study site which is also approved by REHS for blood and saliva processing.
- **Processing:** The research assistants will process and aliquot the blood and oral fluid.
- **Storage:** The specimens will be stored in the -80°C freezer at the lab then transported to Rutgers EOHSI or shipped to the fee for service analytical lab (Comprehensive Laboratory for Untargeted Exposome Science (CLUES), Gangarosa Department of Environmental Health at Emory University) by a research assistant with IATA training.
- **Disposition:** Any excess specimens will be retained by [name] in a -80°C freezer at EOHSI (Room 232). Access to the freezer room is card controlled.

B. Secondary Specimen Collection - NA

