3.0 Multi-Center Research - NA

4.0 Subject Considerations

4.1 Subject Selection and Enrollment Considerations

A. Method to Identify Potential Subjects

Adults who enrolled in the main study who consented to be contacted for future studies will be asked to participate in this study. We will recruit participants from the first and fifth quintiles of PFNA serum concentrations to maximize contrast in exposure, balanced recruitment from the first and fifth quintiles of exposure will be randomized.

B. Recruitment Details

The study will recruit only main study participants. Previous subjects, who completed their main study visit and consented to be contacted for future studies, will be called by a research assistant, and asked if they are interested in participating in a supplemental study. If so, an appointment will be made for a study visit.

C. Subject Screening

Subjects are screened for the main study. Adults who participate in the main study will be eligible for this supplemental study.

- **Inclusion Criteria**
Adults (18 years of age and older), weigh at least 110 pounds, and who participated in the main study may be eligible to participate in this supplemental study.
- **Exclusion Criteria**
 - Pregnancy
 - History of difficult blood draws
 - History of adverse reaction to prior vaccinations
 - Currently taking immune suppressants
 - Recent dental surgery or dental procedure within 4 weeks of starting study
 - Had a Td booster in the past 10 years

D. Privacy Protections

Prospective subjects are identified by their participation in the main study. Identifiers for the main study are stored in the study REDCap database. Only the study team has access to the database.

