6.0 Data Management Plan

6.1 Data Analysis

Means, standard deviations, percentiles and histograms will summarize the distributions of outcome variables. Based on Kielsen (2016), we expect exponential rise in plasma antibody concentrations from 4 to 10 days. Thus, in the primary analysis, we will examine the linear increase in log of antibody concentrations from 4 to 10 days and whether that increase is modified by exposure to pfas through an interaction term between time and PFAS (log-transformed). Integration of exposure, metabolic response, and immune response has the potential to provide key insight into mechanisms underlying

exposure mediated immune suppression following Td vaccine. To examine the assumption that there's a linear increase from 4 to 10 days, linear models with cubic splines relative to time since immunization will assess goodness of fit across different strata of PFAS exposures. If the time of increase varies substantially from the 4 to 10-day assumption, then the initial linear models will be adjusted accordingly.

To investigate associations between RNA-seq and metabolomics data with PFAS exposure levels, differential analysis will identify genes and metabolites with altered expression/abundance across exposure groups. Pathway analysis will assess biological relevance by examining enrichment of gene sets and metabolic pathways. Correlation analysis will evaluate the relationship between individual gene expression/metabolite levels and PFAS exposure. Longitudinal analysis will assess temporal changes in both RNA-seq and metabolomics data following vaccination. Analyses will be adjusted for confounders, corrected for multiple testing, and assume stable PFAS concentrations over time. This comprehensive approach will elucidate the dynamic relationship between molecular profiles and PFAS exposure, advancing our understanding of PFAS toxicity and its impact on human health. For analyzing the oral fluid samples, as a feasibility/proof of concept study, no power calculations have been done. Accuracy will be assessed by comparison to ELISA reference methods by paired t-test and correlation analysis to examine overall bias and reliability. The Bland Altman plot will assess bias and homogeneity of error relative to ELISA across the range of values. Mean, standard deviations, and coefficients of variation will be calculated to benchmark the method for reference in future studies.

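### Only one scheduled visit falls in the primary days 4-10 window, so the time-by-PFAS slope cannot be estimated, and the only repair the plan offers is an open-ended change after PFAS-stratified fits

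*Combined protocol and SAP*

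**What the plan says.** Section 6.1 expects antibody to rise exponentially between days 4 and 10. Its primary analysis is the linear slope of log antibody over that interval and whether log-transformed PFAS modifies it. To check the interval, spline models in time since vaccination "will assess goodness of fit across different strata of PFAS exposures". The next sentence reads: "If the time of increase varies substantially from the 4 to 10-day assumption, then the initial linear models will be adjusted accordingly".

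The visit schedule is in section 1.3: "The second, third, and fourth study visits will occur 24, 48, and 72 hours after the first visit", and "visits five, six, and seven will take place 7, 14, and 30 days after the first visit". With baseline, the draws fall on days 0, 1, 2, 3, 7, 14 and 30. Section 1.8 gives the count as "7 blood samples + 7 saliva samples per subject x 20 subjects". Section 4.1 states: "We will recruit participants from the first and fifth quintiles of PFNA serum concentrations".

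Section 6.1 does not define the strata, say which PFAS they use, or give a threshold, replacement windows or masking. Its sentence on multiple testing belongs to the RNA-seq and metabolomics paragraph.

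**The concern.** There are two linked problems.

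- **The primary model does not fit the schedule.** A slope needs at least two time points, and the stated window contains one. Visits outside the window have to be brought in.
- **The plan's only way of doing so is open-ended and follows sight of the exposure.** PFAS is the modifier under test. If the strata follow the PFNA quintiles used for recruitment, the curves inspected are the exposure contrast itself. Nothing in the text stops the final window from depending on how those curves differ.

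At stake are the error rate of the primary test and its meaning, because different windows are sensitive to different kinds of PFAS effect.

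**Working it through.** **1. The plan's own power figure.** Inputs from section 1.5: n = 20, r = 0.761, and r = 0.7 as the smaller value. Alpha is not stated; two-sided 0.05 is assumed. Power = Φ(atanh(r)·√(n−3) − 1.96).

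- r = 0.761: 0.9986 × 4.123 = 4.117; Φ(2.157) = 98.45% (stated 98.5%).
- r = 0.7: 0.8673 × 4.123 = 3.576; Φ(1.616) = 94.7% (stated 95%).

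Both reproduce. They describe one correlation fixed in advance and make no allowance for a window chosen from the data.

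**2. Visits in the window.** Of days 0, 1, 2, 3, 7, 14 and 30, only day 7 lies in days 4-10. There are 7 × 20 = 140 blood samples, of which 20 are from day 7.

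**3. Estimability.** Let x be log PFAS and E[log antibody] = b0 + b1·t + b2·x + b3·t·x. With t = 7 for everyone this becomes (b0 + 7·b1) + (b2 + 7·b3)·x. Only two combinations of the four coefficients can be estimated (design rank 2 of 4), and neither b1 nor b3 can be separated. Days 3 and 7, or 3, 7 and 14, give rank 4.

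**4. Error rate when the window depends on stratum curves.** The documents give no rule, so this is a simulation on assumptions:

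- 10 participants from the lowest and 10 from the highest quintile of a log-normal PFNA distribution, with no PFNA effect;
- log antibody rises linearly for 6 days from a mean onset of day 4 (onset SD 0.5, 1.0 or 1.5 days);
- median rise 10-fold (SD of the log rise 0.2 or 0.4); residual SD 0.1, 0.3 or 0.5 log units;
- test: two-point slope regressed on log PFNA, two-sided 0.05.

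This makes 3 × 2 × 3 = 18 settings, with 40,000 trials in each.

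| How the window is set | Error rate over 18 settings |
|---|---|
| Fixed in advance | 4.7-5.3% |
| Days 3-7 and 3-14, split alpha | 4.4-5.0% |
| Steepest segment in each stratum; days 3-14 if they disagree | 2.9-5.0% |
| Leave days 3-14 if either stratum is non-linear | 4.9-7.3% |
| Leave days 3-14 if only one stratum is non-linear | 5.3-7.4% |
| Share of rise by day 7 differs by more than 10 points: switch 3-14 to 3-7 | 5.6-8.5% |
| Same trigger: switch 3-7 to 3-14 | 1.7-4.2% |

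The last five rows are assumed rules. None is in the plan.

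**5. What each window can detect.** Take two assumed effects in high PFNA: a log rise smaller by 0.7, or an onset 1.5 days later. Ignoring variation between people, and with ln 10 = 2.30:

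- *Smaller rise.* The full 0.70 difference shows over days 3-14. By day 7 only (7−4)/6 = 50% of the rise has occurred, so days 3-7 show 0.35.
- *Delay.* By day 7 the delayed group has reached (7−5.5)/6 = 25% of its rise against 50%, a difference of 0.25 × 2.30 = 0.58. By day 14 both groups have finished rising (5.5 + 6 = 11.5), so days 3-14 show almost nothing.

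Simulated power in the middle setting (onset SD 1.0, rise SD 0.4, residual SD 0.3):

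| Primary window | Smaller rise | Delay |
|---|---|---|
| Days 3-14 | 65% | 5% |
| Days 3-7 | 24% | 46% |
| Both, split alpha | 56% | 36% |

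**The case against.** **The trigger is about timing, and a fit check within strata is ordinary practice.** This stands in part. The clause turns on when the rise happens, and the text does not say that a difference between strata chooses the window. But it does not exclude this either, and a difference in timing can itself be a PFAS effect: section 1.2 cites an earlier study showing "differences in the time course of production of specific IgG following tetanus-diphtheria (Td) vaccination".

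**Choosing visits because of the schedule is not data-driven.** This stands. The schedule is known now, and naming visits on that ground does not inflate the error rate. It is the reason to do it now and not through the adjustment clause.

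**No visit tolerances are given.** If day-7 visits were spread over several days, a slope could be fitted, but from differences between people and not from each participant's own rise.

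**A stronger reading is tempting:** that analysts will try several windows and keep the most significant. Under assumed curves, taking the smallest p-value of three windows gives about 12%. The plan states no such rule, so that figure is a worst case and not an estimate for this trial.

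**A delayed onset has thin support.** This also stands. Section 1.1 hypothesises a smaller antibody response, and section 1.5 bases power on a "correlation of 0.761 between PFAS level and change in diphtheria antibody concentration". The section 1.2 sentence does not say that onset was later with higher PFAS.

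**Conclusion.** Wrong as written. On the nominal schedule the primary slope and interaction cannot be estimated. This rests only on the visit days and needs no assumption about the curves, beyond visits taking place on their stated days.

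The second part is weaker. Because the primary model may be changed without a rule after PFAS-stratified fits, its nominal error rate is not guaranteed. A reader might infer that the false-positive rate is inflated. The documents do not support that: under the assumed rules the rate fell on both sides of 5% (about 2% to 8.5%), and neither size nor direction can be derived from the plan. The absence of a rule and of masking is judged on the text supplied.

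**What to change.** In section 6.1, before antibody data are analysed against PFAS:

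1. Replace days 4-10 with a window bounded by scheduled visits and named now. Either name one window, for example days 3-14, which suits the smaller response hypothesised in section 1.1 and the antibody change used in section 1.5; or make days 3-7 and days 3-14 co-primary with a stated split of alpha.
2. State that the primary window will not change after PFAS-stratified curves have been seen.
3. Report the PFAS-stratum splines, and any windows they suggest, as labelled sensitivity analyses.

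If the sponsor wants to keep a data-driven change, it should be decided by a written rule from curves pooled over all participants, without PFAS values or quintile. That needs a masked analysis file, because section 1.8 uses the same study ID as the main study.

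The cost is a few sentences, with no new visits or samples. The downside is that the window can no longer be tailored by stratum and that power depends on the form of the effect. Days 3-14 alone gives up nearly all power against a delay. The split-alpha pair recovers much of it and, in the assumed middle setting, gives up 65 − 56 = 9 points of power for a smaller rise.

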1.6 Study Variables

HRP-503a-TEMPLATE-Interventional Research Protocol 1.11.22

Protocol Title: PFAS Exposure and Immune Response

Protocol Version: 3

Protocol Version Date: July 11, 2024

PI: [name], MPH, CIH, DABT

A. Independent Variables, Interventions, or Predictor Variables

Intervention: Participants will be immunized with TENIVAC, which is FDA approved booster vaccine against Tetanus and Diphtheria. Td antibody levels will be measured to determine post-vaccination antibody status.

B. Dependent Variables or Outcome Measures

Tetanus Toxoid IgG, Diphtheria Toxoid IgG, Cytokines, and CRP concentrations in serum and oral fluid. RNA sequencing, and LC/GC-HRMS to identify transcripts and metabolites of immune response in serum.

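### The oral-fluid accuracy analysis uses plain paired methods on up to seven serial pairs per person, with no rule for repeated visits and no named reference specimen

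*Combined protocol and SAP*

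**What the plan says.** The only analysis text for oral fluid is at the end of section 6.1: "Accuracy will be assessed by comparison to ELISA reference methods by paired t-test and correlation analysis to examine overall bias and reliability". A Bland-Altman plot against ELISA follows, then means, SDs and coefficients of variation. The section labels this work as feasibility and gives no power calculation for it. It mentions longitudinal analysis only for RNA-seq and metabolomics.

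The data are serial. Section 1.8 counts "7 blood samples + 7 saliva samples per subject x 20 subjects". Section 1.3 takes both fluids at baseline and at every later visit: three visits at 24, 48 and 72 hours, after which "visits five, six, and seven will take place 7, 14, and 30 days after the first visit".

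The reference specimen is not named. Section 1.6 lists "Tetanus Toxoid IgG, Diphtheria Toxoid IgG, Cytokines, and CRP concentrations in serum and oral fluid", and section 1.2 says "OF has been shown to be a reliable biomatrix for detecting antibodies that represent serum concentrations". Both make serum the more natural reading, but neither states it as the reference. Section 1.2 also grants that antibody levels tend to be lower in oral fluid. It gives the intended use: "as a less burdensome method, compared to venipuncture, for serial measurement of immune responses in epidemiological studies".

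**The concern.** Two separate problems can arise if the 140 pairs are analysed as one sample.

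- **Standard error.** A person whose oral-fluid result is offset from the reference at one visit will tend to be offset at the next. Seven such differences carry less information than seven independent ones, so a pooled paired t-test is too ready to declare bias.
- **Correlation, IgG with a serum reference only.** Section 6.1 expects antibody to rise steeply between days 4 and 10. If oral fluid rises too, that common time course enters a pooled r whether or not people with high serum values also have high oral-fluid values. The pooled r cannot separate the two. The documents give no oral-fluid time course for cytokines or CRP, so this part is limited to IgG.

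The result will be used: "If found to be feasible and reliable in this study, this method will be useful in future community-based studies of immune response". A later study that replaces blood with oral fluid needs to know what kind of agreement was shown.

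**Working it through.** **Counts.** (7 + 7) × 20 = 280 specimens, as section 1.8 states. Pairs: 7 × 20 = 140.

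**Paired t-test.** Assume no true bias and an ICC of the differences within a person. The documents give no ICC, so a range is used. The design effect is 1 + (7 − 1) × ICC, and the approximate rejection rate is 2 × [1 − Φ(1.96 / √design effect)].

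| ICC | Design effect | Effective pairs (140 / design effect) | Approximate rejection | Simulated (20,000 runs) |
|---|---|---|---|---|
| 0.1 | 1.6 | 87.5 | 12% | 11.8% |
| 0.3 | 2.8 | 50 | 24% | 23.9% |
| 0.5 | 4.0 | 35 | 33% | 33.2% |
| 0.7 | 5.2 | 26.9 | 39% | 39.7% |

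On the 20 person-mean differences the simulated rate is 4.9% to 5.0%. These rates assume no true bias, so they fit an ELISA on the same oral fluid. They do not fit a serum reference, where a level gap is expected.

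**Bland-Altman.** In the same simulations the pooled SD of differences averages 0.996, 0.992, 0.985 and 0.980 of its true value, so the point limits are at most 2% too narrow.

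**Pooled IgG correlation, serum reference.** All inputs are assumptions except the visit days and the day 4 to 10 window. The log10 serum rise is L × (0, 0, 0, 0, 0.5, 1, 1) over the seven visits; day 7 gets (7 − 4)/(10 − 4) = 0.5. The variance of this profile is 2.25/7 − (2.5/7)² = 0.194. Oral fluid rises by a × L, SD is the same in both fluids, and rho is the true same-visit correlation. Then

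pooled r = (0.194 × a × L² + rho × SD²) / √[(0.194 × L² + SD²) × (0.194 × a² × L² + SD²)].

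Example with L = 1, SD = 0.5, a = 1, rho = 0: 0.194 / (0.194 + 0.25) = 0.44.

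| L, SD | rho 0: a = 1 | a = 0.5 | a = 0 | rho 0.5: a = 1 | a = 0.5 | a = 0 |
|---|---|---|---|---|---|---|
| 0.5, 0.5 | 0.16 | 0.09 | 0 | 0.58 | 0.53 | 0.46 |
| 0.5, 0.3 | 0.35 | 0.20 | 0 | 0.68 | 0.58 | 0.40 |
| 1.0, 0.5 | 0.44 | 0.27 | 0 | 0.72 | 0.61 | 0.38 |
| 1.0, 0.3 | 0.68 | 0.49 | 0 | 0.84 | 0.72 | 0.28 |

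An r at a single visit would be about 0 or 0.5 throughout. The pooled r can lie above or below it.

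**Levels and change are different questions.** Take 70% of the variance as between persons. If the fluids agree only between persons (0.5), the visit-centred or day-14 r is 0.7 × 0.5 = 0.35 (simulated 0.34), while the r of day 0 to day 14 change is 0 (simulated −0.01). If they agree only within persons (0.5), the level r is 0.3 × 0.5 = 0.15 (simulated 0.15 to 0.16), while the change r is 0.5 (simulated 0.49). In this model everyone has the same mean rise, so the change r equals the within-person correlation. Neither figure stands in for the other.

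**Precision.** For r = 0.5 at n = 20, Fisher z gives 0.549 ± 1.96/√17, that is 0.074 to 1.025, or r from 0.07 to 0.77. For a visit-centred r, a nominal 95% CI from resampling participants covers 92% to 93% in simulation. Treating the 140 pairs as independent gives 64% to 67%.

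**The case against.** The strongest reply is that pooling is not written anywhere. A competent analyst could go visit by visit or add a person effect, and for a feasibility aim outside the two objectives the plan need not spell this out. The consequences also split by reading: the t-test rates need a same-fluid ELISA, the correlation point needs serum, and each needs pooling. All of this stands, and it is why the point is minor and conditional. The feasibility label explains the missing power calculation. It does not settle the unit of analysis, and the named methods in their plain form assume independence.

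A reader might infer that the plan would wrongly certify oral fluid as ranking people correctly. The documents do not support that. No section requires ranking, and the stated use is serial measurement, for which tracking the rise is part of what is wanted. A pooled r is then incomplete, not wrong. Zero agreement between people is an extreme case that section 1.2 gives no reason to expect. Nor is the pooled r always inflated: it falls below the same-visit value when oral fluid does not rise.

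It is also fair that a paired comparison with serum is informative as an estimate. Section 1.2 expects a gap but gives no size. Only a test of zero difference adds little there.

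**Conclusion.** The concern holds as a minor one. Section 6.1 names methods that in plain form assume independent pairs, for data with up to seven serial pairs per person, and nothing else in the documents covers this clustering for oral fluid.

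If pairs are pooled and there is no true bias, the nominal 5% paired t-test has a true rate of about 12% to 40% over an assumed ICC of 0.1 to 0.7. If the reference is serum, a pooled IgG r cannot by itself separate time-course tracking from agreement between people. The size and sign of that effect rest on the assumed fold rise, spread and oral-fluid response. Bland-Altman point limits are nearly unaffected.

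It would be too strong to say that the oral-fluid results will be invalid: that assumes a pooled analysis the plan does not state. The primary antibody analysis is not touched.

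**What to change.** In section 6.1:

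1. Name the reference specimen and analyse on the log scale.
2. Estimate bias and limits of agreement with a participant random effect (repeated-measures Bland-Altman). As a minimum, run the paired t-test on the 20 person-mean differences. With a serum reference, report the mean log difference with its CI as an estimate of the gap.
3. Report correlation separately for levels (at fixed visits, or centred on the visit mean) and for change from baseline (for example day 0 to day 14 or day 30), with CIs from resampling participants. Label a visit-centred r as a blend of between-person and within-person agreement, and any pooled r as time-course tracking. The change correlation is the one relevant to objective 1 in section 1.1, which concerns changes in antibody levels.

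The cost is a few sentences and slightly more analysis, with no new samples. The intervals will be wide at n = 20, as the 0.07 to 0.77 example shows, and the participant-resampling CI falls slightly short of its nominal coverage. Both should be stated with the results.

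### The oral-fluid accuracy analysis names neither its reference specimen nor a log or ratio scale, so its paired t-test and Bland-Altman plot may not show how well oral fluid agrees with the reference

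*Combined protocol and SAP*

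**What the plan says.** The oral-fluid analysis is in section 6.1 (Data Analysis): "Accuracy will be assessed by comparison to ELISA reference methods by paired t-test and correlation analysis to examine overall bias and reliability". The next sentence reads: "The Bland Altman plot will assess bias and homogeneity of error relative to ELISA across the range of values". Means, standard deviations and coefficients of variation are also planned. No scale, limits of agreement or acceptance limit is given, and the specimen on which the reference ELISA is run is not named. On sample size, this part is described "as a feasibility/proof of concept study, no power calculations have been done".

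Three other places bear on the point.

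- Section 1.2 (Research Significance) gives the purpose, a less burdensome substitute for repeated venipuncture. It states that "OF has been shown to be a reliable biomatrix for detecting antibodies that represent serum concentrations", and continues: "even though antibodies in this fluid are often found in lower concentrations when compared to serum". It gives no ratio.
- Section 1.6 (Study Variables) lists "Tetanus Toxoid IgG, Diphtheria Toxoid IgG, Cytokines, and CRP concentrations in serum and oral fluid", so the same markers are measured in both fluids.
- For the primary model, section 6.1 does state a scale: "we will examine the linear increase in log of antibody concentrations from 4 to 10 days". It does not extend this to the oral-fluid comparison.

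**The concern.** A paired t-test on concentrations asks whether the two means are equal. If the reference is serum, section 1.2 already leads one to expect that they are not, and a significant result says nothing about whether oral fluid could stand in for serum. A raw-scale Bland-Altman plot has a related weakness: when one fluid is a small fraction of the other, the difference is nearly the serum value itself, so the plot shows a steep trend whether or not oral fluid carries information.

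If the reference is ELISA on the same oral fluid, equal means are a reasonable target. Non-significance with few pairs is still weak evidence of agreement, and antibody errors that grow with level would let the highest values set the raw-scale limits.

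At stake is the pilot's use. Section 6.1 wants figures that later studies can refer to, and section 1.2 wants to know whether oral fluid can replace serial blood draws.

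**Working it through.** **The plan's own figures.** None exists for oral fluid. The only power figures are in section 1.5, for the PFAS-antibody correlation. By Fisher's z with two-sided alpha 0.05 (assumed), r = 0.761 and n = 20 give atanh(0.761) × √17 − 1.96 = 0.9986 × 4.123 − 1.96 = 2.157, or 98.45% power against the stated 98.5%. For r = 0.7 the result is 94.7% against 95%. Both reproduce, but they concern a different analysis.

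**Inputs.** The documents give 20 subjects, and section 1.8 gives the specimen count: "In total there will be 280 specimens collected for this study (7 blood samples + 7 saliva samples per subject x 20 subjects". That is 140 blood and oral-fluid pairs. The check uses one pair per person (20 pairs), so it does not depend on how repeat visits are handled. Assumed, because the documents give no values: oral-fluid/serum ratio k; log-SD of serum IgG 0.5 to 1.0; oral-fluid log-noise SD 0.3, which represents good tracking.

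**Serum reference, raw scale, no noise.** With O = kS, the difference is O − S = −(1 − k)S and the mean is (1 + k)S/2. The Bland-Altman slope is therefore −2(1 − k)/(1 + k):

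- k = 0.5: −1.0/1.5 = −0.67
- k = 0.1: −1.8/1.1 = −1.64
- k = 0.01: −1.98/1.01 = −1.96
- k = 0.001: −1.998/1.001 = −2.00

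**Serum reference, raw scale, with noise 0.3 (simulated, 20 lognormal pairs).**

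| k | Paired t-test rejects | Correlation of difference with mean |
|---|---|---|
| 1 | about 3-6% | 0.2 to 0.3 |
| 0.8 | about 49-70% | −0.03 to −0.31 |
| 0.5 | 98-100% | −0.66 to −0.86 |
| 0.1 or less | 99-100% | −0.99 to −1.00 |

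At k = 0.5 the plot is a trend with scatter. At k = 0.1 or less it is almost a line set by serum.

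**Does the raw analysis separate good from useless?** Oral fluid simulated as unrelated to serum at k = 0.01 gave 99-100% rejection and slope −2.00. Oral fluid that tracks serum gave 99-100% and −1.96. At k = 0.1 the figures were 98-100% with slope about −1.9 (unrelated) and 99-100% with slope about −1.6 (tracking).

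**Same-specimen reference.** The level difference disappears. Suppose the method is unbiased but very noisy, with log-SD 1.0. Its ratio limits of agreement are exp(±1.96 × 1.0), or 0.14 to 7.1. The raw paired t-test on 20 pairs is still non-significant in roughly 87-92% of studies, depending on the spread of true values and on whether unbiased refers to the mean or the median. If error is proportional to level, a specimen with ten times the antibody has ten times the SD of difference, so the highest post-booster values set the raw limits. Section 6.1 itself expects an exponential antibody rise.

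**Log scale.** The log difference is log k + e, where e is the noise. Its mean recovers k: geometric mean ratios of 0.80, 0.50, 0.10 and 0.01 were returned. Its SD recovers the noise, about 0.30, giving limits around the ratio of exp(±1.96 × 0.3), or 0.56 to 1.80. The plot's slope no longer depends on k. It is (0.09/2)/(SD² + 0.09/4), or 0.165 at log-SD 0.5 and 0.044 at log-SD 1.0, a small residue of putting all the noise in one fluid. A log-scale t-test of no difference still rejects in 88-89% at k = 0.8 and 100% at k ≤ 0.5. The log scale therefore repairs the plot but does not make the zero-difference test useful against serum.

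**Fold-change.** log(O_t/O_1) = log(kS_t/kS_1) = log(S_t/S_1), so a constant ratio cancels.

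**The case against.** The strongest reply is that the serum reading is an inference. Section 6.1 speaks of reference methods and of benchmarking, which fits ELISA on the same oral fluid at least as well. Under that reading the slopes and the 98-100% rejection do not apply. This stands, and it is why the point is conditional and why naming the specimen comes first.

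A reader might also infer four stronger things that the documents do not support.

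- *That bias against serum is certain.* Section 1.2 says lower levels are frequent, not universal, and gives no ratio. At k = 0.8, rejection is only about 49-70%.
- *That the plot cannot measure accuracy.* This applies to a raw-scale plot against serum at low k. The plan is silent on scale and does not prescribe the raw scale; a log plot gives an interpretable ratio and limits. A check for homogeneity of error could itself prompt a change of scale.
- *That the plan must declare oral fluid biased.* It has no decision rule or acceptance limit here, and it does not say that a non-significant t-test will be read as accuracy.
- *That the plan ignores tracking.* Correlation is planned and is unaffected by a constant ratio. It does not, however, give limits of agreement.

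Finally, this is a pilot aim. That limits the consequence, but choosing an interpretable summary costs very little.

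**Conclusion.** The point holds as a conditional one. With a serum reference and oral-fluid IgG at about half of serum or less, a raw paired t-test finds a difference in about 98-100% of 20-pair studies even with good tracking. At about a tenth or less, the raw plot mainly re-expresses the serum level. With a same-specimen reference the level argument falls, but the t-test p-value remains a poor measure of accuracy and raw limits remain dominated by high values. These sizes rest on assumed ratios, spreads and noise, and on lognormal data with proportional error. The documents supply none of these. Log-scale ratios with limits of agreement are better under either reading. The change is worth making, but it concerns a feasibility aim and does not touch the primary PFAS-antibody analysis.

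**What to change.** In section 6.1:

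1. Name the reference specimen and assay for the oral-fluid comparison.
2. Replace the paired t-test p-value and any raw-scale Bland-Altman plot with log-scale differences. Report the geometric mean ratio with its confidence interval and ratio limits of agreement. Keep the correlation as a description of tracking.
3. If the reference is serum, also calibrate log oral-fluid IgG to log serum IgG and give ratio limits for the calibrated value. Compare log fold-change from visit 1 between the fluids, mainly at days 7, 14 and 30. The 24, 48 and 72 hour visits precede the 4 to 10 day antibody rise that section 6.1 expects and may carry little antibody signal. Step 3 does not apply if the reference is ELISA on the same oral fluid.

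The cost is SAP wording and minor reprogramming, with no new samples or assays for the log-scale analysis. The downside is that calibrated limits estimated in the same 20 people are slightly optimistic; the report should label them so.
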